6.2.5 Definitions of dose limiting toxicities (DLTs)

A dose-limiting toxicity (DLT) is defined as an adverse event or abnormal laboratory value assessed as unrelated to disease progression, inter-current illness, or concomitant medications that meets any of the following criteria in [Table 6-3](#).

For the purpose of dose escalation decisions, only DLTs occurring during the first 6 weeks of study treatment will be necessarily considered and included in the BLRM.

[figure not shown]
Toxicity will be assessed using the NCI Common Terminology Criteria for Adverse Events, version 4.03 (evs.nci.nih.gov/ftp1/CTCAE) unless otherwise specified.

The investigator must notify the Sponsor immediately of any unexpected CTCAE grade ≥ 3 adverse events or laboratory abnormalities. Prior to enrolling patients into a higher dose level, CTCAE grade ≥ 2 adverse events will be reviewed for all patients at the current dose level.

For toxicities which, by definition, require a time-window in order to be defined as DLTs (grade 3 non-hematologic toxicity for ≥ 7 consecutive days), a subsequent visit and/or laboratory assessments must be scheduled accordingly. For example, if a grade 3 non-hematologic toxicity is observed, it must also be observed at least 7 days later, with no intervening lower grades, in order to qualify as a DLT.

Table 6-3 Criteria for defining dose-limiting toxicities

| TOXICITY | DLT CRITERIA |
|---|--|
| Hematologic | |
| Blood and lymphatic system disorders | Neutropenia CTCAE Grade 4* |
| | Febrile neutropenia CTCAE Grade ≥ 3 (ANC $< 1.0 \times 10^9/L$ + Fever ≥ 38.5 degrees C) |
| | Thrombocytopenia CTCAE Grade 4 (Platelets $< 25 \times 10^9/L$)* |
| | Hemorrhagic Event CTCAE Grade ≥ 2 |
| | Anemia CTCAE Grade 4 for ≥ 7 days despite PRBC transfusions |
| Non-Hematologic | |
| Gastrointestinal disorders | Vomiting CTCAE Grade ≥ 3 for > 7 days in duration |
| | Nausea CTCAE Grade 3 despite the use of anti-emetic therapy |
| Hepatic | Total bilirubin CTCAE Grade ≥ 3 , with Direct Bilirubin ≥ 0.5 mg/dL |
| | AST/SGOT or ALT/SGPT CTCAE Grade 3 for ≥ 5 consecutive days |
| | AST/SGOT or ALT/SGPT CTCAE Grade 4 |
| CK elevation | CTCAE Grade ≥ 3 |
| Other | Any CTCAE Grade 3 non-hematologic toxicity for ≥ 7 days Any CTCAE Grade 4 non-hematologic toxicity |
| CTCAE version 4.03 will be used for all grading. | |
| * In two consecutive assessments (the second assessment will be considered valid and final) | |

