Appropriate eligibility criteria and specific DLT definitions, as well as specific dose modification and stopping rules are included in this protocol.

Patients who experience a DLT will have their therapy with LDE225 and INC424 interrupted and will be followed as described in [Table 6-4](#). After recovery from the toxicity in question, if the Investigator believes that it is in the patient's best interest to resume therapy with LDE225 and INC424, the patient may resume therapy, only after consultation with the Sponsor, according to the guidelines described in [Section 6.3.1](#) and [Table 6-4](#).

However, the patient must be permanently discontinued from study medication and withdrawn from the study, if any of the following DLTs occur:

- any grade ≥ 3 hemorrhagic event
- grade 4 anemia for ≥ 7 consecutive days despite PRBC transfusions
- 2nd episode of grade ≥ 3 febrile neutropenia
- grade 3 renal toxicity for ≥ 7 consecutive days
- grade 4 renal toxicity
- grade 4 non-hematologic toxicity

If during the first 6 weeks a patient misses > 10 doses of LDE225 or > 20 doses of INC424, the patient will not be evaluable for DLTs. The patient can continue in the study, but another patient has to be enrolled at the same dose level in order to reach the required minimum number of patients in the cohort.

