6.3 Dose modifications

6.3.1 Dose modification and dose delay

For patients who do not tolerate the protocol-specified dosing schedule, dose adjustments are permitted in order to allow the patient to continue the study treatment. The following guidelines need to be applied. Any plan to deviate from these guidelines in view of patient safety must be discussed with the sponsor unless there is an urgent need for action.

All dose modifications should be based on the worst preceding toxicity as graded by the NCI Clinical Toxicity Criteria (NCI-CTCAE version 4.03). If study treatment is held due to toxicity, scheduled visits and all assessments as described in [Table 7-1](#) should continue as scheduled, except without dosing. Dose modification guidelines are described in [Table 6-4](#).

If an adverse event is clearly associated to one of study drugs, the dose adjustment directed for that study drug will be followed; however, if the causality is not clear, then it may be necessary to adjust both study drugs. Dosing adjustments will be discussed with the sponsor.

If a patient experiences a DLT then treatment with LDE225 plus INC424 must be stopped and the patient may be discontinued from the study. However, following resolution of the DLT to CTCAE grade 1 or to the patient's baseline value, the patient may continue to receive study treatment at a reduced combination dose level, if appropriate, at the discretion of the investigator and after discussion with the Sponsor.

For each patient, a maximum of 2 dose reductions will be allowed, after which the patient will be required to discontinue study treatment. If the same toxicity returns after re-initiation of treatment at the same dose level, the second re-initiation must resume at a lower dose level. The patient must also discontinue study treatment if, after the treatment is resumed at the lower dose level, the same toxicity recurs with the same or worse severity (except for thrombocytopenia, anemia and neutropenia).

Dose level (-1) is the lowest acceptable dosing level for a patient participating in the study. If a patient cannot tolerate dose level (-1), then study treatment must be discontinued and the patient must be withdrawn from the study. However, if patients in Cohort 1 experience thrombocytopenic DLTs then patients in dose level (-1) will receive INC424 5mg BID and LDE225 200 mg QD.

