If a patient requires a dose delay from either study drug of > 21 days due to an LDE225 or INC424 related toxicity, then the patient must be discontinued from the study; however, if the patient is obtaining clinical benefit in terms of response, the patient may continue treatment at the same or at a reduced dose following discussion between the investigator and Novartis. All patients will be followed for AEs and SAEs for 30 days following the last dose of LDE225 and/or INC424.

Dose modifications for toxicities occurring during the DLT-definition period (6 weeks or 42 days) will not be allowed unless the toxicity qualifies as a DLT. After a toxicity has been characterized as a DLT, a patient can resume therapy with a reduced treatment dose according to the guidelines provided in [Section 6.2.5.1](#).

If the administration of study treatment was interrupted for reasons other than toxicity, then treatment with LDE225 and INC424 may be resumed at the same dose.

Patients who experience muscle toxicity, regardless of whether the toxicity meets the criteria described for a DLT, should be followed according to the dosing modifications for LDE225 as per [Table 6-5](#).

Patients who experience hematologic, renal, or hepatic toxicities should receive follow up evaluations as outlined in [Table 6-7](#).

All interruptions or changes to study drug administration must be recorded on the Dosage and Administration Record eCRF.

[figure not shown]

Table 6-4 Criteria for interruption and re-initiation of INC424 and LDE225 treatment

| | |
|--|---|
| Dose modifications for toxicities occurring during the DLT-definition period (6 weeks or 42 days), and considered as treatment-related, will not be allowed until the toxicity qualifies as a DLT. | |
| Worst toxicity (CTCAE 4.03 Grade) | Dose Modifications for INC424 and LDE225 |
| HEMATOLOGICAL | |
| Neutropenia (ANC) (for 2 consecutive assessments within 48 hrs except febrile neutropenia) | |
| Grade 1 (ANC < LLN - $1.5 \times 10^9/L$) Grade 2 (ANC < $1.5 - 1.0 \times 10^9/L$) Grade 3 (ANC < $1.0 - 0.5 \times 10^9/L$) | INC424: Maintain dose level LDE225: Maintain dose level |
| Grade 4 (ANC < $0.5 \times 10^9/L$) | INC424: Hold dose until resolved to \leq grade 1, then maintain dose level LDE225: Hold dose until resolved to \leq grade 1, then maintain dose level |

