| Dose modifications for toxicities occurring during the DLT-definition period (6 weeks or 42 days), and considered as treatment-related, will not be allowed until the toxicity qualifies as a DLT. | |
| Worst toxicity (CTCAE 4.03 Grade) | Dose Modifications for INC424 and LDE225 |
| Grade 3 | INC424: Hold dose until resolved to \leq grade 1, then \downarrow by 5 mg BID LDE225: Hold dose until resolved to \leq grade 1, then \downarrow by 1 dose level |
| Grade 4 | INC424: Discontinue study treatment LDE225: Discontinue study treatment |
| Common Terminology Criteria for Adverse Events (CTCAE) version 4.03. Hold dose for \geq Grade 3 vomiting or Grade 3 nausea only if the vomiting or nausea cannot be controlled with optimal antiemetic. If the investigator deems that a recommended dose reduction or the recommendation to maintain the same dose is not in the best interest of the patient, this decision may be discussed with Novartis on a case-by-case basis. | |

Table 6-5 Recommended LDE225 dose modifications and dose delays for suspected treatment-related muscle toxicities

| Severity of CK elevation | Dose modifications and management recommendations |
|---|---|
| Asymptomatic CK elevation | |
| Grade 2 [CK elevation $>2.5 \times$ ULN - $5 \times$ ULN] | 
 Continue treatment on the same dose and monitor CK levels weekly until resolution to baseline level. Check renal function (serum creatinine) regularly and ensure that patient is adequately hydrated. |
| Symptomatic (new-onset or worsening of pre-existing muscle symptoms such as myalgia, myopathy, and/or spasms) CK elevation | |
| Grade 1 [CK elevation $>$ ULN - $2.5 \times$ ULN] | 
 Continue treatment at the same dose and monitor CK levels weekly until resolution to baseline level and then monthly thereafter. Monitor muscle symptoms for changes until resolution to baseline. Check renal function (serum creatinine) regularly and ensure that patient is adequately hydrated. |
| Grade 2 [CK elevation $>2.5 \times$ ULN - $5 \times$ ULN] | 
 Interrupt treatment and monitor CK levels weekly until resolution to baseline level. Monitor muscle symptoms for changes until resolution to baseline. Upon resolution, resume treatment at the reduced dose level and measure CK monthly thereafter. Check renal function (serum creatinine) regularly and ensure that patient is adequately hydrated. |

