| Asymptomatic or Symptomatic CK elevation | |
| Grade 3 or 4 without renal impairment [Grade 3 (CK elevation $>5 \times$ ULN - $10 \times$ ULN)] [Grade or 4 (CK elevation $>10 \times$ ULN)] | 
 Interrupt treatment and monitor CK levels weekly until resolution to baseline level. Monitor muscle symptoms for changes until resolution to baseline. Check renal function (serum creatinine) regularly and ensure that patient is adequately hydrated. If renal function is not impaired (normal serum creatinine) and CK resolves to baseline level, consider resuming treatment at a reduced dose. CK levels should be measured weekly for 2 months after re-administration of sonidegib and monthly thereafter. |
| Grade 3 or 4 with renal impairment | 
 Interrupt treatment and monitor CK levels weekly until resolution to baseline level. Monitor muscle symptoms for changes until resolution to baseline. If renal function is impaired ($\geq 50\%$ above the baseline level), interrupt treatment. Ensure patient is adequately hydrated and evaluate other secondary causes. Continue monitoring of CK and creatinine levels weekly. If CK levels return to baseline level and creatinine levels return to baseline, consider resuming treatment at the reduced dose otherwise discontinue treatment permanently. |

Table 6-6 Dose restart guidelines and allowed maximum doses for patients who have previously interrupted dose for grade 4 thrombocytopenia and grade 4 neutropenia

[figure not shown]
| Current PLT Count | ▼ Dose Restart or Dose Increase Guidelines ▼ | |
|-----------------------------------|--|--------------------------------|
| | INC424 | LDE 225 |
| < 50 x10 ⁹ /L | Continue to hold | Continue to hold |
| 50 to < 75 x10 ⁹ /L | Restart at 5 mg BID for at least 14 days If stable, may increase to 10 mg BID or original dose (whichever is lower) | Restart at original dose level |
| 75 to < 100 x10 ⁹ /L | Restart at 10 mg BID for at least 14 days If stable, may increase to 15 mg BID or original dose, (whichever is lower) | Restart at original dose level |
| 100 to < 125 x10 ⁹ /L | Restart at original dose | Restart at original dose level |
| ≥ 125 x10 ⁹ /L | Restart at original dose | Restart at original dose level |
| Current ANC Level | ▼ Dose Restart or Dose Increase Guidelines ▼ | |
| < 0.5 x10 ⁹ /L | Continue to hold | Continue to hold |

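### For a Grade 3 or higher CK elevation, the protocol stops both drugs in some passages and refers the patient to an LDE225-only table in others, with no rule of precedence; at Grade 4 the passages conflict directly

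*Protocol*

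**What the plan says.** Protocol Table 6-3 lists "CK elevation | CTCAE Grade ≥ 3" as a DLT, with no duration condition.

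Two passages then act on both drugs:
- Section 6.2.5: "Patients who experience a DLT will have their therapy with LDE225 and INC424 interrupted". It sends the patient to Table 6-4 for follow-up.
- Section 6.3.1: "If a patient experiences a DLT then treatment with LDE225 plus INC424 must be stopped". Treatment may restart later at a reduced combination dose level.

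Two other rules in section 6.3.1 point to a single drug:
- Attribution: "If an adverse event is clearly associated to one of study drugs, the dose adjustment directed for that study drug will be followed".
- Muscle toxicity: such patients, "regardless of whether the toxicity meets the criteria described for a DLT, should be followed according to the dosing modifications for LDE225" in Table 6-5.

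Table 6-5 is titled "Recommended LDE225 dose modifications and dose delays for suspected treatment-related muscle toxicities". For Grade 3 or 4 CK elevation its action is "Interrupt treatment and monitor CK levels weekly until resolution to baseline level", and it then allows resumption at a reduced dose to be considered. It has no INC424 line.

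At Grade 4, three places require discontinuation for non-hematologic toxicity in general: the permanent-discontinuation list in section 6.2.5, the row of Table 6-4 for other non-hematological events, and section 7.1.3.

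**The concern.** All of these instructions reach the same patient. The muscle-toxicity rule expressly includes DLTs, so DLT status does not separate it from the both-drugs rules. The event is foreseeable: protocol section 1.4.1.2.1 describes CK elevation as the dose-limiting toxicity of LDE225.

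What is at stake is patient safety and drug exposure. The text does not settle whether INC424 is held during a CK event or, at Grade 4, whether treatment may resume at all. INC424 is the partner with established spleen activity (41.9% against 0.7% on placebo at Week 24, Table 1-6), and the Phase II primary endpoint is a single-arm spleen response rate. Exposure that depends on which passage is followed is therefore undesirable.

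**Working it through.** The plan gives no figure for this point. The check is a comparison of passages, followed by simple arithmetic on exposure.

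**1. Passages side by side, CK elevation of Grade 3 or higher**

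| Place (protocol) | LDE225 | INC424 |
|---|---|---|
| 6.2.5, DLT rule | interrupt | interrupt |
| 6.3.1, DLT rule | stop; may restart at a reduced combination level | same |
| 6.3.1, attribution rule | adjust, if clearly due to LDE225 | not addressed |
| 6.3.1, muscle-toxicity rule | follow Table 6-5 | not addressed |
| Table 6-5 | interrupt; consider resuming at a reduced dose | no instruction |
| Table 6-4, other non-hematological, Grade 3 | hold, then down one level | hold, then down 5 mg BID |

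Table 6-4, to which section 6.2.5 refers, has no CK row. The word treatment in Table 6-5 is ambiguous: section 6.1 defines study treatment as the combination, but the table's title names LDE225 and its re-administration text names sonidegib only. Recovery criteria also differ: Grade 1 or baseline in the 6.3.1 DLT rule, baseline in Table 6-5. Section 4.3.1 ties the two drugs together for permanent discontinuation only. No passage states precedence.

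**2. Grade 4 CK elevation**

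- Section 6.2.5, Table 6-4 and section 7.1.3: discontinue for Grade 4 non-hematologic toxicity.
- Table 6-5: after Grade 3 or 4 CK elevation without renal impairment, resumption may be considered once CK returns to baseline. With renal impairment, it may be considered once CK and creatinine both return to baseline.

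**3. Size of the INC424 difference between the interruption readings**

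Inputs: 24 weeks × 7 = 168 days to the endpoint; CK DLTs resolved in 4-8 weeks, or 28-56 days, on single-agent LDE225 (section 1.4.1.2.1); a delay of either drug beyond 21 days leads to discontinuation unless the patient is benefiting in terms of response (sections 6.3.1 and 7.1.3); permanent discontinuation of one drug ends both (section 4.3.1).

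- Default: if only LDE225 is held, the 21-day limit then ends both drugs. The readings differ by at most about 21 days: 21/168 = 12.5%.
- Response exception granted: 28/168 = 16.7% to 56/168 = 33.3%.

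These figures count days off drug. They do not count a lower INC424 dose after restart, nor the Grade 4 choice between ending treatment and possibly resuming it.

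**4. Patients affected**

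The documents give no CK rate for the combination. Single-agent Grade 3 or 4 rates in Table 1-2 are 0/5 at 400 mg QD and 2/26 = 7.7% at 800 mg QD (one Grade 3, one Grade 4). The Amendment 2 rationale confirms the RPIID with LDE225 at 400 mg QD. For 0/5, the exact upper 95% limit is 1 − 0.025^(1/5) = 0.52, so that row neither shows nor excludes a material rate.

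**The case against.** The strongest defence is that the passages can be read together: the DLT rule holds both drugs, and Table 6-5 adds LDE225 monitoring and restart. A reader might infer that the protocol tells sites to continue INC424 through a CK DLT. It does not. Neither LDE225-directed rule excludes action on INC424, and the undifferentiated wording of Table 6-5 can cover both drugs. That reading is available but nowhere stated, and it does not resolve Grade 4.

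At Grade 4, one could treat the CK text as a specific exception. Section 7.1.3 has its own CK item (renal impairment without return to baseline), which would be redundant at Grade 4 if the general rule already applied. But the unqualified Grade 4 rule stands in the same list, and nothing marks the CK item as an exception.

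Sponsor involvement also counts. Section 6.3.1 has dosing adjustments discussed with the sponsor, and section 6.2.5 requires consultation before resumption. So it is not established that sites would act differently, although consultation supplies no rule.

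The link to the primary endpoint is weak as well. Section 6.2.5 sits under dose escalation, and the dose-determining set is Phase Ib only, whereas the Week 24 spleen-volume endpoint is primary in Phase II. Section 6.3.1 is not limited to Phase Ib.

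**Conclusion.** The inconsistency is real and should be corrected. For CK elevation of Grade 3 or higher, the both-drugs rules and the referral to Table 6-5 apply together without a stated order, and INC424 is left unaddressed in that table. At Grade 4, mandatory discontinuation and permitted resumption contradict each other.

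The INC424 exposure difference is up to about 21 days (12.5% of 168) by default, and 28-56 days (17-33%) only where the response exception is granted. The longer range assumes that the single-agent LDE225 resolution time carries over to the combination.

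Two stronger inferences are not supported:
- That up to 18% of patients are affected. The 19/103 behind that figure pools doses up to 3000 mg QD and 750 mg BID, and 15 of the 19 events were Grade 4. The rate at the RPIID is unknown.
- That the Week 24 response rate is biased or power is lost by a known amount. The documents give no spleen regrowth after an INC424 hold; section 6.3.1.1 speaks of returning symptoms only.

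**What to change.** Reconcile sections 6.2.5, 6.3.1 and 7.1.3 with Tables 6-4 and 6-5:
- State which passage takes precedence for a CK DLT, separately for Grade 3 and Grade 4.
- In Table 6-5, give an explicit line for INC424 as well as LDE225, as Table 6-4 does, and replace the bare word treatment with the drug or drugs meant.
- Use one recovery criterion, or say why two apply.

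The clinical team decides which rule governs; this review takes no position on it. The cost is wording in a protocol amendment, with no change to sample size, endpoints or the analysis.

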6.2.5.1 Follow-up for dose-limiting toxicities

Patients whose treatment is discontinued or interrupted due to a DLT, must be followed until resolution or stabilization of the DLT event, whichever comes first, as described in [Section 6.3.1](#).

In case of a hemorrhagic event, of any grade (CTCAE grade 1 included), the Investigator is advised to perform coagulation tests and an albumin assessment.

Additional guidance on the management of grade 4 thrombocytopenia and grade 4 neutropenia is described in [Section 6.3.2](#).

6.3 Dose modifications

6.3.1 Dose modification and dose delay

For patients who do not tolerate the protocol-specified dosing schedule, dose adjustments are permitted in order to allow the patient to continue the study treatment. The following guidelines need to be applied. Any plan to deviate from these guidelines in view of patient safety must be discussed with the sponsor unless there is an urgent need for action.

All dose modifications should be based on the worst preceding toxicity as graded by the NCI Clinical Toxicity Criteria (NCI-CTCAE version 4.03). If study treatment is held due to toxicity, scheduled visits and all assessments as described in [Table 7-1](#) should continue as scheduled, except without dosing. Dose modification guidelines are described in [Table 6-4](#).

If an adverse event is clearly associated to one of study drugs, the dose adjustment directed for that study drug will be followed; however, if the causality is not clear, then it may be necessary to adjust both study drugs. Dosing adjustments will be discussed with the sponsor.

If a patient experiences a DLT then treatment with LDE225 plus INC424 must be stopped and the patient may be discontinued from the study. However, following resolution of the DLT to CTCAE grade 1 or to the patient's baseline value, the patient may continue to receive study treatment at a reduced combination dose level, if appropriate, at the discretion of the investigator and after discussion with the Sponsor.

For each patient, a maximum of 2 dose reductions will be allowed, after which the patient will be required to discontinue study treatment. If the same toxicity returns after re-initiation of treatment at the same dose level, the second re-initiation must resume at a lower dose level. The patient must also discontinue study treatment if, after the treatment is resumed at the lower dose level, the same toxicity recurs with the same or worse severity (except for thrombocytopenia, anemia and neutropenia).

Dose level (-1) is the lowest acceptable dosing level for a patient participating in the study. If a patient cannot tolerate dose level (-1), then study treatment must be discontinued and the patient must be withdrawn from the study. However, if patients in Cohort 1 experience thrombocytopenic DLTs then patients in dose level (-1) will receive INC424 5mg BID and LDE225 200 mg QD.

If a patient requires a dose delay from either study drug of > 21 days due to an LDE225 or INC424 related toxicity, then the patient must be discontinued from the study; however, if the patient is obtaining clinical benefit in terms of response, the patient may continue treatment at the same or at a reduced dose following discussion between the investigator and Novartis. All patients will be followed for AEs and SAEs for 30 days following the last dose of LDE225 and/or INC424.

Dose modifications for toxicities occurring during the DLT-definition period (6 weeks or 42 days) will not be allowed unless the toxicity qualifies as a DLT. After a toxicity has been characterized as a DLT, a patient can resume therapy with a reduced treatment dose according to the guidelines provided in [Section 6.2.5.1](#).

If the administration of study treatment was interrupted for reasons other than toxicity, then treatment with LDE225 and INC424 may be resumed at the same dose.

Patients who experience muscle toxicity, regardless of whether the toxicity meets the criteria described for a DLT, should be followed according to the dosing modifications for LDE225 as per [Table 6-5](#).

Patients who experience hematologic, renal, or hepatic toxicities should receive follow up evaluations as outlined in [Table 6-7](#).

All interruptions or changes to study drug administration must be recorded on the Dosage and Administration Record eCRF.

[figure not shown]

Table 6-4 Criteria for interruption and re-initiation of INC424 and LDE225 treatment

| | |
|--|---|
| Dose modifications for toxicities occurring during the DLT-definition period (6 weeks or 42 days), and considered as treatment-related, will not be allowed until the toxicity qualifies as a DLT. | |
| Worst toxicity (CTCAE 4.03 Grade) | Dose Modifications for INC424 and LDE225 |
| HEMATOLOGICAL | |
| Neutropenia (ANC) (for 2 consecutive assessments within 48 hrs except febrile neutropenia) | |
| Grade 1 (ANC < LLN - $1.5 \times 10^9/L$) Grade 2 (ANC < $1.5 - 1.0 \times 10^9/L$) Grade 3 (ANC < $1.0 - 0.5 \times 10^9/L$) | INC424: Maintain dose level LDE225: Maintain dose level |
| Grade 4 (ANC < $0.5 \times 10^9/L$) | INC424: Hold dose until resolved to \leq grade 1, then maintain dose level LDE225: Hold dose until resolved to \leq grade 1, then maintain dose level |
| Febrile neutropenia (Grade \geq 3) (ANC < $1.0 \times 10^9/L$, with a single temperature of ≥ 38.3 °C or a sustained temperature of ≥ 38 °C for more than one hour) | INC424: Discontinue study treatment LDE225: Discontinue study treatment |
| Thrombocytopenia (for 2 consecutive assessments within 48 hrs) | |
| Grade 1 (PLT < LLN - $75 \times 10^9/L$) | INC424: Maintain dose level LDE225: Maintain dose level |
| Grade 2 (PLT < $75 - 50 \times 10^9/L$) | INC424: Reduce to 10 mg BID or continue at same dose level (whichever is lower) LDE225: Maintain dose level |
| Grade 3 (PLT < $50-25 \times 10^9/L$) | INC424: Reduce to 5mg BID LDE225: Maintain dose level |
| Grade 4 (PLT < $25 \times 10^9/L$) | INC424: Hold dose until resolved to \leq grade 1, then maintain dose level LDE225: Hold dose until resolved to \leq grade 1, then maintain dose level |
| Hemorrhagic event of any kind (if related to study treatment) | |
| Grade 1 | INC424: Maintain dose level LDE225: Maintain dose level |
| Grade 2 | INC424: Hold dose until resolved completely, then \downarrow by 5 mg BID LDE225: Hold dose until resolved completely, then maintain dose level |
| Grade 3 or 4 | INC424: Discontinue study treatment LDE225: Discontinue study treatment |
| RENAL | |
| Serum creatinine | |
| < 2 x ULN | INC424: Maintain dose level LDE225: Maintain dose level |
| 2 – 3 x ULN | INC424: Hold dose until resolved to \leq grade 1, then: If resolved in \leq 7 days, then maintain dose level If resolved in > 7 days, then \downarrow by 5 mg BID LDE225: Hold dose until resolved to \leq grade 1, then: If resolved in \leq 7 days, then maintain dose level If resolved in > 7 days, then \downarrow 1 dose level |
| Grade 3 (> $3.0 - 6.0 \times ULN$) | INC424: Discontinue study treatment LDE225: Discontinue study treatment |
| Grade 4 (> $6.0 \times ULN$) | INC424: Discontinue study treatment LDE225: Discontinue study treatment |

| | |
|--|---|
| Dose modifications for toxicities occurring during the DLT-definition period (6 weeks or 42 days), and considered as treatment-related, will not be allowed until the toxicity qualifies as a DLT. | |
| Worst toxicity (CTCAE 4.03 Grade) | Dose Modifications for INC424 and LDE225 |
| HEPATIC | |
| Bilirubin (*for patients with Gilbert Syndrome these dose modifications apply to changes in direct bilirubin only). Bilirubin will be fractionated if elevated | |
| Up to 2.0 x ULN | INC424: Maintain dose level LDE225: Maintain dose level |
| > 2.0 – 3.0 x ULN with ALT or AST ≤ 3.0 x ULN | INC424: Hold dose until resolved to ≤ grade 1, then: If resolved in ≤ 7 days, then maintain dose level If resolved in > 7 days, then ↓ by 5 mg BID LDE225: Hold dose until resolved to ≤ grade 1, then: If resolved in ≤ 7 days, then maintain dose If resolved in > 7 days, then ↓ 1 dose level |
| > 3.0 - 10.0 x ULN with ALT or AST ≤ 3.0 x ULN | INC424: Hold dose until resolved to ≤ grade 1, then: If resolved in ≤ 7 days, then maintain dose level If resolved in > 7 days, then discontinue treatment LDE225: Hold dose until resolved to ≤ grade 1, then ↓ 1 dose level |
| > 10.0 x ULN | INC424: Discontinue study treatment LDE225: Discontinue study treatment |
| AST or ALT | |
| Grade 1 (> ULN – 3.0 x ULN) | INC424: Maintain dose level LDE225: Maintain dose level |
| Grade 2 (> 3.0 - 5.0 x ULN) without total bilirubin elevation to > 2.0 x ULN | INC424: Maintain dose level LDE225: Maintain dose level |
| Grade 3 (> 5.0 - 20.0 x ULN) without total bilirubin elevation to > 2.0 x ULN | INC424: Hold dose until resolved to ≤ grade 1, then: If resolved in ≤ 7 days, then maintain dose level If resolved in > 7 days, then ↓ by 5 mg BID LDE225: Hold dose until resolved to ≤ grade 1, then ↓ 1 dose level |
| Grade 4 (> 20.0 x ULN) without bilirubin elevation to > 2.0 x ULN | INC424: Hold dose until resolved to ≤ grade 1, then ↓ by 5 mg BID LDE225: Hold dose until resolved to ≤ grade 1 or baseline, then ↓ 1 dose level |
| CARDIAC | |
| Cardiac – QTc prolongation | |
| QTcF > 500 ms (≥ Grade 3) or > 60 ms change from baseline on at least two separate ECGs | Perform an analysis of serum potassium and magnesium, and if below lower limit of normal, correct with supplements to within normal limits. Concomitant medication usage must be reviewed. Perform a repeat ECG within one hour of the first QTcF of > 500 ms. If QTcF remains > 500 ms, repeat ECG as clinically indicated but at least once a day until the QTcF returns to < 480 ms. INC424: Hold dose until QTcF prolongation has resolved, then ↓ by 5 mg BID LDE225: Hold dose. Once QTcF prolongation has resolved, study treatment may be restarted at ↓ 1 dose level Second Occurrence: Discontinue patient from further study treatment with both medications |
| Other non- hematological adverse events | |
| Grade 1 or 2 | INC424: Maintain dose level LDE225: Maintain dose level |

| | |
|---|--|
| Dose modifications for toxicities occurring during the DLT-definition period (6 weeks or 42 days), and considered as treatment-related, will not be allowed until the toxicity qualifies as a DLT. | |
| Worst toxicity (CTCAE 4.03 Grade) | Dose Modifications for INC424 and LDE225 |
| Grade 3 | INC424: Hold dose until resolved to \leq grade 1, then \downarrow by 5 mg BID LDE225: Hold dose until resolved to \leq grade 1, then \downarrow by 1 dose level |
| Grade 4 | INC424: Discontinue study treatment LDE225: Discontinue study treatment |
| Common Terminology Criteria for Adverse Events (CTCAE) version 4.03. Hold dose for \geq Grade 3 vomiting or Grade 3 nausea only if the vomiting or nausea cannot be controlled with optimal antiemetic. If the investigator deems that a recommended dose reduction or the recommendation to maintain the same dose is not in the best interest of the patient, this decision may be discussed with Novartis on a case-by-case basis. | |

Table 6-5 Recommended LDE225 dose modifications and dose delays for suspected treatment-related muscle toxicities

| Severity of CK elevation | Dose modifications and management recommendations |
|---|---|
| Asymptomatic CK elevation | |
| Grade 2 [CK elevation $>2.5 \times$ ULN - $5 \times$ ULN] | 
 Continue treatment on the same dose and monitor CK levels weekly until resolution to baseline level. Check renal function (serum creatinine) regularly and ensure that patient is adequately hydrated. |
| Symptomatic (new-onset or worsening of pre-existing muscle symptoms such as myalgia, myopathy, and/or spasms) CK elevation | |
| Grade 1 [CK elevation $>$ ULN - $2.5 \times$ ULN] | 
 Continue treatment at the same dose and monitor CK levels weekly until resolution to baseline level and then monthly thereafter. Monitor muscle symptoms for changes until resolution to baseline. Check renal function (serum creatinine) regularly and ensure that patient is adequately hydrated. |
| Grade 2 [CK elevation $>2.5 \times$ ULN - $5 \times$ ULN] | 
 Interrupt treatment and monitor CK levels weekly until resolution to baseline level. Monitor muscle symptoms for changes until resolution to baseline. Upon resolution, resume treatment at the reduced dose level and measure CK monthly thereafter. Check renal function (serum creatinine) regularly and ensure that patient is adequately hydrated. |
| Asymptomatic or Symptomatic CK elevation | |
| Grade 3 or 4 without renal impairment [Grade 3 (CK elevation $>5 \times$ ULN - $10 \times$ ULN)] [Grade or 4 (CK elevation $>10 \times$ ULN)] | 
 Interrupt treatment and monitor CK levels weekly until resolution to baseline level. Monitor muscle symptoms for changes until resolution to baseline. Check renal function (serum creatinine) regularly and ensure that patient is adequately hydrated. If renal function is not impaired (normal serum creatinine) and CK resolves to baseline level, consider resuming treatment at a reduced dose. CK levels should be measured weekly for 2 months after re-administration of sonidegib and monthly thereafter. |
| Grade 3 or 4 with renal impairment | 
 Interrupt treatment and monitor CK levels weekly until resolution to baseline level. Monitor muscle symptoms for changes until resolution to baseline. If renal function is impaired ($\geq 50\%$ above the baseline level), interrupt treatment. Ensure patient is adequately hydrated and evaluate other secondary causes. Continue monitoring of CK and creatinine levels weekly. If CK levels return to baseline level and creatinine levels return to baseline, consider resuming treatment at the reduced dose otherwise discontinue treatment permanently. |

Table 6-6 Dose restart guidelines and allowed maximum doses for patients who have previously interrupted dose for grade 4 thrombocytopenia and grade 4 neutropenia

[figure not shown]
| Current PLT Count | ▼ Dose Restart or Dose Increase Guidelines ▼ | |
|-----------------------------------|--|--------------------------------|
| | INC424 | LDE 225 |
| < 50 x10 ⁹ /L | Continue to hold | Continue to hold |
| 50 to < 75 x10 ⁹ /L | Restart at 5 mg BID for at least 14 days If stable, may increase to 10 mg BID or original dose (whichever is lower) | Restart at original dose level |
| 75 to < 100 x10 ⁹ /L | Restart at 10 mg BID for at least 14 days If stable, may increase to 15 mg BID or original dose, (whichever is lower) | Restart at original dose level |
| 100 to < 125 x10 ⁹ /L | Restart at original dose | Restart at original dose level |
| ≥ 125 x10 ⁹ /L | Restart at original dose | Restart at original dose level |
| Current ANC Level | ▼ Dose Restart or Dose Increase Guidelines ▼ | |
| < 0.5 x10 ⁹ /L | Continue to hold | Continue to hold |
| 0.5 to < 0.75 x10 ⁹ /L | 5 mg BID for at least 2 weeks; if stable, may increase to 10 mg BID or original dose, (whichever is lower) | Restart at original dose level |
| 0.75 to <1 x10 ⁹ /L | 10 mg BID for at least 2 weeks; if stable, may increase to 15 mg BID or original dose, (whichever is lower) | Restart at original dose level |
| 1 to < 1.5 x10 ⁹ /L | Restart at original dose | Restart at original dose level |
| ≥ 1.5 x10 ⁹ /L | Restart at original dose | Restart at original dose level |

